The total required sample size for this study is **458 patients**. Assumptions for the power analysis include non-inferiority for VAP recurrence and superiority for antibiotic-free days in the intervention group, 3 planned analyses of the data with O'Brien-Fleming spending function with binding futility boundaries, 25% recurrence rate in the control group (14), and 6 enrolling centers with an average cluster size of 10. To detect a 10% difference in outcomes between groups with 80% power and assuming a 10% dropout rate, a total sample size of 458 patients is required for this study. Sample size will be recalculated at each interim analysis with better estimates based on accrued patients. The planned analyses will take place after enrollment of 150, 300, and all patients.

VII. Study-Wide Recruitment Methods

This is a multicenter randomized controlled trial. We have partnered with the Surgical Infection Society to aid in recruitment of interested centers for participation in the study. The recruitment methods for individual subjects to participate in the study will be uniform across all centers. A member of the research team at each center will screen all patients in their respective surgical ICUs by reviewing the medical record of each patient in the ICU for eligibility based on the inclusion and exclusion criteria listed in *Section V* (above). Screening will occur daily during the study period. We will be requesting a waiver of the requirement for written authorization

UM IRB No.: 20211211

NCT05545735

Protocol Date: November 14, 2023

Principal Investigator: [name]., M.S.P.H.

Study Title: The Duration of Antibiotic Therapy for Early VAP (DATE) Trial

from patients to access their health records due to the nature of the study. Please see further documentation in *Section XXXII* (below).

VIII. Study Timeline

Each individual patient enrolled in the study will be followed for 30 days or until hospital discharge, whichever occurs first. We will also review patient charts at hospital discharge to determine overall hospital length of stay and overall mortality, in addition to 30-day outcomes. We expect all subjects to be enrolled within the first 2 years of study across all centers, with full data analysis completed at 3 months after study completion.

IX. Study Endpoints

A) Primary Outcomes

- a.** VAP recurrence within 30 days
 - i.** VAP recurrence = VAP occurring 2 – 14 days following completion of initial therapy

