- b.** Antibiotic-free days within 30 days

B) Secondary Outcomes

- a.** Antibiotic exposure
 - i.** Days of antibiotics
 - ii.** Antibiotic days (defined as the product of days of antibiotics and number of antibiotics per day)
- b.** Clinical improvement, measured using daily CPIS_{clinical} score while enrolled in the study
- c.** VAP relapse = recurrent VAP caused by initial pathogen (if culture data available), occurring 2 – 14 days following completion of initial therapy
- d.** 30-day Ventilator-free days

UM IRB No.: 20211211

NCT05545735

Protocol Date: November 14, 2023

Principal Investigator: [name]., M.S.P.H.

Study Title: The Duration of Antibiotic Therapy for Early VAP (DATE) Trial

- e. Empyema
- f. Need for tracheostomy
- g. Non-pulmonary infections
- h. 30-day ICU-free days
- i. Hospital LOS
- j. In-hospital Mortality

X. Procedures Involved

This is a multicenter, randomized, clinical trial. The trial will be reported in accordance with the recommendations of the CONSORT statement (18). IRB approval will be obtained. All subjects, or their legally authorized representatives, will provide written consent for study participation. The trial is registered with the US National Institutes of Health (ClinicalTrials.gov Identifier #NCT05545735).

Screening will occur daily by study personnel. Eligible patients will be approached as soon as possible after inclusion criteria are met (i.e., 1 – 3 days prior to randomization). Randomization will occur using a computer-generated block pattern no later than the end of the fourth day of appropriate antibiotic therapy. Randomization will occur at the hospital level in blocks of 20.

Empiric antibiotic therapy will be instituted as soon as possible following diagnosis of suspected pneumonia by the clinical team. The default antibiotic will be based on the local institutional antibiogram and practice. Pre-existing treatment for a non-pulmonary infection with at least one antibiotic that has appropriate activity against the VAP pathogen may be substituted for the default antibiotic. Once sensitivity data become available, therapy may be de-escalated to a more narrow-spectrum agent, as indicated.

The default duration of antibiotic therapy will be determined by study group assignment; the treatment team will be asked to adhere to study group assignment whenever possible. However, the treatment team may choose to extend the duration of antibiotic therapy based on

UM IRB No.: 20211211

NCT05545735

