excluded). Data will be expressed as median (interquartile range) or frequency (%). Normality of continuous variables will be assessed by visual inspection of histograms. Differences in the means of continuous normally distributed variables will be assessed using Student's t-test or ANOVA. Differences in the medians of non-normally distributed continuous variables will be assessed using the Wilcoxon rank sum or Kruskal-Wallis tests. Proportions will be compared using the chi-squared or Fischer's exact test, as appropriate. Univariate analysis of categorical outcomes will be expressed as the relative risk with 95% confidence intervals, with standard errors adjusted for intra-center clustering. A generalized estimating equation or linear mixed model (with appropriate transformation of outcome variables to approximate normality, if needed) will be fit to address possible confounding if randomization fails to assure equitable distribution. Baseline variables associated with randomization status at the $p < 0.25$ level by univariate analysis will be added to the model using a stepwise selection method. The overall contribution of the fitted model to predicting variability in the outcome of interest will be assessed using the likelihood ratio chi-squared test. The alpha error level is defined at 0.05, with statistical significance at $p < 0.05$. No adjustment for multiplicity of outcomes will be done as this is an exploratory (rather than confirmatory) trial, and all hypotheses are pre-planned. Adjustment for multiple comparisons in pre-planned hypotheses leads to more type II errors (19, 20).

XIII. Provisions to Monitor the Data to Ensure the Safety of Subjects

As mentioned previously (see *Section X*), a DSMB will be convened. The DSMB will meet after each planned interim analysis, review data collected across all sites, and submit a written report to the overall study PI, who will submit the report to the IRB. Data analysis will be performed by [name], as mentioned above (see *Section XII*).

Data will be monitored daily at each site and any adverse events will be reported to the site PI per local IRB regulations. Efficacy and safety data will be collected on CRFs and inputted into REDCap by study personnel at each site. The study will be terminated early if there are

UM IRB No.: 20211211

NCT05545735

Protocol Date: November 14, 2023

Principal Investigator: [name]., M.S.P.H.

Study Title: The Duration of Antibiotic Therapy for Early VAP (DATE) Trial

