unacceptably high rates of adverse events or if there is a clear benefit noted in either study group, as deemed by the DSMB.

XIV. Withdrawal of Subjects

Subjects, or their legally authorized representatives, can withdrawal from the study at any time. If a subject wishes to withdraw from the study, we will request their permission to allow us to continue collecting data to use in the intention-to-treat analysis. As previously mentioned (see *Section X*), the clinical team may choose to continue antibiotic therapy despite the subject's study group allocation. Clinical decision-making will supersede any study procedures or protocols.

XV. Risks to Subjects

There is a risk that a default of 4 days of antibiotic therapy will be too short. In order to mitigate this risk, clinical endpoints will be followed daily during treatment. If any of these endpoints suggest inadequate therapy, the treatment team may choose to extend the duration of treatment. This decision will take precedence over study group assignment.

XVI. Potential Benefits to Subjects

The most significant potential direct benefit to subjects enrolled in this study is the possibility of limiting days of antibiotic exposure. Limiting the number of days receiving antibiotic therapy may decrease the subjects' individual risk of developing *Clostridium difficile* colitis, a common and potentially life-threatening consequence of antibiotic exposure. Similar multicenter randomized controlled trials aimed at limiting antibiotic days in patients with intra-abdominal infections have recently been published, with the University of Miami as a participating center, and have shown a benefit to shorter antimicrobial therapy, including less antibiotic days without increase in infectious complications (21).

UM IRB No.: 20211211

NCT05545735

Protocol Date: November 14, 2023

Principal Investigator: [name]., M.S.P.H.

Study Title: The Duration of Antibiotic Therapy for Early VAP (DATE) Trial

XVII. Vulnerable Populations

Our research does not involve pregnant women, neonates, children, or prisoners. In potential subjects being mechanically ventilated and cognitively impaired, their LAR will be approached to provide informed consent.

XVIII. Multi-Site Research

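### With 25% recurrence in both arms, 458 patients give about 76% or 65% power for non-inferiority, not 80%, and the cluster size of 10 does not fit 458

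*Combined protocol and SAP*

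**What the plan says.** Section VI (Number of Subjects) sets out the framework: "Assumptions for the power analysis include non-inferiority for VAP recurrence and superiority for antibiotic-free days in the intervention group". The other inputs are three analyses with O'Brien-Fleming spending and binding futility, and "25% recurrence rate in the control group (14), and 6 enrolling centers with an average cluster size of 10". It gives 458 as the total to enroll, on these design targets: "To detect a 10% difference in outcomes between groups with 80% power and assuming a 10% dropout rate".

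On timing, the same section says "The planned analyses will take place after enrollment of 150, 300, and all patients", and that the sample size will be recalculated at each interim analysis.

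Three other sections bear on the calculation:

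- Section XII (Data Management): "The alpha error level is defined at 0.05", with no statement of one- or two-sided.
- Sections X and XII: "Randomization will occur at the hospital level in blocks of 20".
- Section XIV (Withdrawal of Subjects), on subjects who withdraw: "we will request their permission to allow us to continue collecting data to use in the intention-to-treat analysis".

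The rate assumed in the 4-day arm, a margin named as such, the futility spending function and an intraclass correlation (ICC) do not appear with these inputs.

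**The concern.** The hypothesis in Section III is that 4 days is non-inferior to 7 days for recurrence. The natural planning case is that the two durations are equivalent, with 25% recurrence in each arm. In that case 458 looks too small for 80% power with a 10-point margin once 10% dropout is taken off. The wording about detecting a 10% difference also raises the possibility that a different test was sized.

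If 4 days really is equivalent, the chance of failing to show non-inferiority would be about one in four (one-sided 5%) or one in three (one-sided 2.5%), rather than the one in five that the ethics board and the DSMB are told. An inconclusive result could then be misread as evidence against short therapy.

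The cluster input looked wrong on its face, because 6 centers of 10 patients do not make 458.

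**Working it through.** **Inputs from the plan.** Control recurrence 25%, difference 10%, power 80%, dropout 10%, total 458, looks at 150, 300 and all patients (Section VI); alpha 0.05 (Section XII).

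**Assumptions where the plan is silent.** The 10% is an absolute non-inferiority margin. Recurrence is 25% in both arms. Allocation is 1:1. Alpha is either one-sided 5% (z = 1.645) or one-sided 2.5% (z = 1.960). Pairs below are in that order.

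**1. Trying to reproduce 458.**

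n per arm = (z_α + z_β)² × (2 × 0.25 × 0.75) / 0.10², with z_β = 0.842.

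- One-sided 5%: 231.8, so 232 per arm and 464 evaluable; 464/0.9 = 516 enrolled.
- One-sided 2.5%: 294.3, so 295 per arm and 590 evaluable; 590/0.9 = 656 enrolled.

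Neither enrolled figure is 458, and neither yet allows for interim looks.

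**2. Power at 458 enrolled.** 458 × 0.9 = 412 evaluable, 206 per arm. The standard error is √(0.375/206) = 0.0427, and 0.10/0.0427 = 2.344.

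- Φ(2.344 − 1.645) = 75.8%
- Φ(2.344 − 1.960) = 64.9%

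**3. Adding the looks.** Information fractions are 150/458 = 0.328, 300/458 = 0.655 and 1. These rows use numerical integration with Lan-DeMets O'Brien-Fleming alpha spending. The futility rows use O'Brien-Fleming-type beta spending, which is an assumption.

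| Design, 25% in both arms | One-sided 5% | One-sided 2.5% |
|---|---|---|
| 412 evaluable, fixed | 75.8% | 64.9% |
| 412 evaluable, efficacy looks | about 75% | about 64% |
| 412 evaluable, looks and binding futility | about 73–74% | about 60–64% |
| 458 evaluable (no data lost), fixed | 79.6% | 69.5% |
| 458 evaluable, efficacy looks | about 79% | about 69% |
| Enrolled for 80%, fixed | 516 | 656 |
| Enrolled for 80%, efficacy looks | about 526 | about 662 |
| Enrolled for 80%, looks and binding futility | about 551 | about 693 |

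**4. Sensitivity to the 4-day rate p** (412 evaluable, fixed design). Power = Φ((0.10 − (p − 0.25)) / √((0.1875 + p(1 − p))/206) − z_α).

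| True 4-day rate | One-sided 5% | One-sided 2.5% |
|---|---|---|
| 23% | 88.6% | 81.4% |
| 24% | 82.9% | 73.8% |
| 25% | 75.8% | 64.9% |
| 26% | 67.4% | 55.4% |

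Power reaches 80% at a 4-day rate of 24.4% or 23.2%. With looks and binding futility the thresholds are about 24.1% or 22.9%.

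**5. Calculations that land near 458.**

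- Non-inferiority at one-sided 5% with neither dropout nor looks: 464.
- Superiority, 25% versus 15%, one-sided 5%: 390 to 394 evaluable in a fixed design (unpooled or pooled variance). Multiplying by 1.069 for looks and binding futility gives about 416 to 421, and dividing by 0.9 gives about 462 to 468 enrolled. Power for this comparison at 412 evaluable is about 80%.
- Non-inferiority with looks, binding futility and dropout, but with a better 4-day arm: about 449 enrolled at 24% (one-sided 5%) or about 468 at 23% (one-sided 2.5%).

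The plan documents none of these.

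**6. Clusters.** 6 × 10 = 60 patients. Going the other way, 458/6 = 76.3 per center, or 458/10 = 45.8 clusters. Sixty patients would not reach the first look at 150. Ten patients would also leave a center's first block of 20 incomplete; that is possible in practice but sits oddly with the design. With no ICC given, the effect on power cannot be computed.

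**The case against.** The strongest reply is that the shortfall depends on an input the plan never states. Section VI gives only the control rate. If the 4-day rate is just 0.6 points lower (24.4%), fixed-design power at one-sided 5% is back to 80%, and 458 can be reached within a non-inferiority calculation. On this view the supportable complaint is missing inputs, not a wrong figure. This stands in part: the margin, the sidedness and the 4-day rate are assumptions, and the power figures are conditional on them. It does not rescue the 80%, because that reading requires the shorter course to be truly better, which the plan does not assume, and power drops to 67.4% or 55.4% if it is one point worse.

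A second reply is that withdrawn subjects may still contribute data under Section XIV. Even if nothing is lost, power is 79.6% or 69.5% before the looks, and Section VI says that 458 already allows for dropout.

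A third is that the sample size will be recalculated and that Section XII calls the trial exploratory. The recalculation has no stated rule, and it needs a defined margin, alpha and 4-day rate to start from. The exploratory label is offered there as a reason not to adjust for multiplicity. Neither makes the stated power correct.

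On clusters, the term is not defined, and with randomization within hospital a full design effect would overstate the loss. Any site numbers under Section XXI (Setting) were not available to this review. Those limits are accepted, so no power loss is claimed from clustering. The mismatch itself lies within Section VI.

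**Conclusion.** The concern holds. With an absolute 10-point margin and 25% recurrence in both arms, 458 enrolled does not give 80% power for the non-inferiority test under either reading of alpha: 75.8% or 64.9% before the looks, and about 73–74% or 60–64% with the looks and binding futility. The last range depends on a futility spending function that the plan does not give. The fixed-design shortfall is about 4 or 15 percentage points (80 − 75.8 = 4.2; 80 − 64.9 = 15.1).

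How 458 was obtained cannot be established from the plan. If it came from 25% versus 15%, the 80% refers to showing that 4 days lowers recurrence by 10 points, which is not the hypothesis.

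If a cluster is a center, an average size of 10 in 6 centers cannot be reconciled with 458 patients or with a first look at 150.

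**What to change.** In Section VI:

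- State which test was sized, the non-inferiority margin, the one-sided alpha, the assumed 4-day recurrence rate and the futility spending function.
- Restate the power for 458 enrolled and 412 evaluable under those inputs. With a 10-point margin and 25% in both arms, it is about 75% or lower at one-sided 5%, or about 64% or lower at one-sided 2.5%, after the looks.
- If 458 came from 25% versus 15%, say so and report the non-inferiority power separately.
- Correct or remove the average cluster size of 10 so that it agrees with 458 patients in 6 centers (about 76 each), and give the ICC if a design effect was used.

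This changes text in Section VI only and requires no added patients. The cost is a less favourable stated power. Keeping 80% at equal rates would instead mean enrolling the larger numbers shown in the working, which is a separate decision for the investigators.

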Protocol Date: November 14, 2023

Principal Investigator: [name]., M.S.P.H.

Study Title: The Duration of Antibiotic Therapy for Early VAP (DATE) Trial

clinical circumstances, such as deterioration in hemodynamic or respiratory status that is believed to be related to incompletely treated VAP, or continued treatment of a non-pulmonary infection. The treatment team may also decide to extend the duration of antibiotic therapy based on the results of procalcitonin measurements, if obtained. Clinical decisions will take precedence over study group assignment.

Patients will be followed for 30 days or until hospital discharge, whichever occurs first. Please see the attached data collection tool for detailed information.

Adverse event monitoring will occur daily at each individual institution. Any adverse event will trigger notification to the site PI per local IRB regulations. The safety of the study will be monitored by an independent Data Safety Monitoring Board (DSMB). The DSMB has been formed by the Surgical Infection Society and will consist of Drs. [name], [name], and [name]. The committee will meet after each planned interim analysis (see *Sections VI and XII*) and submit a written report to the overall study PI ([name]), who will submit to the IRB (see attached “*DSMB Charter*”).

Disease Related Adverse Events: It is recognized that this patient population who require critical care support will experience a number of common aberrations in laboratory values, signs, and symptoms due to the severity of the underlying disease and the impact of standard therapies. These will not necessarily constitute an AE unless they:

- require significant intervention,
- lead to discontinuation of study procedures,
- felt to be related to study procedures
- or are considered to be of concern, in the Investigator’s clinical judgment.

Examples of the type of AEs that may be associated with the patient population are acute respiratory failure; respiratory distress; acute lung injury; acute respiratory distress syndrome (ARDS); acute renal failure; fever, bacteremia; sepsis, septic shock; hypotension; metabolic acidosis, pleural effusion; mineral or electrolyte imbalance. For purposes of this study, deaths

UM IRB No.: 20211211

NCT05545735

Protocol Date: November 14, 2023

Principal Investigator: [name]., M.S.P.H.

Study Title: The Duration of Antibiotic Therapy for Early VAP (DATE) Trial

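### Daily CPIS has no named summary and no assured adjustment for CPIS at randomization; an unconditional baseline-adjusted comparison over one common window would be more precise

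*Combined protocol and SAP*

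**What the plan says.** Section IX, secondary outcome b, takes CPIS each day "score while enrolled in the study". It gives no time point, baseline, summary or contrast. Section VIII bounds enrolment: "Each individual patient enrolled in the study will be followed for 30 days or until hospital discharge, whichever occurs first". The number of scores therefore differs between patients. Section X sets randomization "no later than the end of the fourth day of appropriate antibiotic therapy", so a score from before randomization can exist.

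Section XII is the only analysis text. Normally distributed continuous variables get a t-test or ANOVA. For the rest: "Differences in the medians of non-normally distributed continuous variables will be assessed using the Wilcoxon rank sum or Kruskal-Wallis tests". A GEE or linear mixed model is named, but it "will be fit to address possible confounding if randomization fails to assure equitable distribution". Its covariates are baseline variables associated with arm at p<0.25, added stepwise. The one clustering adjustment stated for the unadjusted comparisons is for center and applies to relative risks. Repeated scores within a patient are not mentioned.

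**The concern.** A two-sample test needs one number per patient, and the plan does not say how a series of daily scores becomes one. The choice of day or window is therefore open until the data are seen, in a plan that makes no multiplicity adjustment across outcomes.

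Scores within a patient are correlated, so CPIS at randomization predicts later CPIS. Leaving it out of the comparison gives up precision that the daily scoring already makes available. The plan's model does not fill this gap, because it is triggered by imbalance. Under sound randomization a baseline variable passes a p<0.25 screen in about one trial in four, and stepwise selection may still drop it.

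CPIS is the plan's day-by-day measure of recovery, and Section XV names too short a course as the risk of the 4-day arm. A less precise analysis makes slower recovery in that arm easier to miss.

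**Working it through.** The documents state no figure for CPIS, so there is none to reproduce. The check asks how much precision baseline adjustment recovers.

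**Inputs**
- From Section VI: 458 patients, 10% dropout, 80% power. 458 × 0.9 = 412.2, so 206 per arm.
- From Section XII: alpha 0.05, taken as two-sided because sidedness is not stated.
- Assumed: CPIS in SD units; correlation between days either constant (r = 0.3, 0.5, 0.7) or decaying as AR(1) with 0.8 per day; baseline is the day-4 score; a true difference of 0.2 SD on the affected days; complete scores; interim looks ignored.

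**1. Detectable difference on a single day**

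Detectable difference = 2.802 × √(2v/206), with v = 1 unadjusted and v = 1 − r² adjusted for baseline.

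| Analysis | v | Detectable difference (SD) |
|---|---|---|
| Unadjusted | 1 | 0.276 |
| Adjusted, r = 0.3 | 0.91 | 0.263 |
| Adjusted, r = 0.5 | 0.75 | 0.239 |
| Adjusted, r = 0.7 | 0.51 | 0.197 |

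**2. Power for the mean of days 5-10, effect on those days**

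Power = Φ(effect/√(2v/206) − 1.96). The adjusted v is the unadjusted v minus c², where c is the covariance of the mean with baseline.
- Constant r = 0.5: v = (1 + 5 × 0.5)/6 = 0.583, SE 0.0753, power Φ(2.658 − 1.96) = 0.76. Adjusted: v = 0.583 − 0.25 = 0.333, SE 0.0569, power Φ(3.516 − 1.96) = 0.94.
- AR(1) 0.8: v = 0.680, SE 0.0813, power 0.69. Adjusted: c = 0.492, v = 0.680 − 0.242 = 0.438, SE 0.0652, power 0.87.

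**3. A longer window: mean of days 5-18, effect on days 8-18**

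The effect on the mean is 0.2 × 11/14 = 0.157 SD.
- Constant r = 0.5: v falls from 0.536 to 0.286; power rises from 0.59 to 0.85.
- AR(1) 0.8: v falls from 0.448 to 0.373; power rises from 0.66 to 0.74. The gain is smaller because day 4 says less about later days.

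**4. Choice of window (adjusted, constant r = 0.5)**
- Effect on days 8-18 seen through the day 5-10 mean: effect 0.2 × 3/6 = 0.10 SD, SE 0.0569, power 0.42, against 0.85 for the day 5-18 mean.
- Effect on days 5-10 seen through the day 5-18 mean: effect 0.2 × 6/14 = 0.086 SD, SE 0.0527, power 0.37, against 0.94 for the day 5-10 mean.

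No window is best for every effect timing.

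**5. Simulation**

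A simulation used 2,000 runs per setting and enrolment spread uniformly over 10-30 days, independent of arm. It crossed four summaries, three effect timings and five correlation structures (60 settings). ANCOVA had higher power than the t-test in all 60. The smallest gain was 0.532 to 0.554 (day 10 alone, AR(1) 0.8, effect on days 5-10). The largest was 0.417 to 0.876 (day 5-18 mean, r = 0.7, effect on days 8-18). Type I error of both analyses was 0.042-0.056.

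**The case against.** The strongest reply is that nothing here is invalid. A two-sample test of one summary per patient keeps its level, this is one of ten lettered secondary outcomes, and Section XII calls the trial exploratory. Section XII also names a mixed model and would often admit a clearly unbalanced baseline CPIS. All of this stands, and it limits the point to precision. It does not remove the point, because adjustment that waits for imbalance forgoes the gain whenever the arms look balanced. The correlations are assumed, and the gain shrinks in longer windows when correlation decays.

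A reader might infer three stronger things that the documents do not support.
- *CPIS scoring stops with antibiotics, so the arms are scored over 4 and 7 days.* Section XV does say "clinical endpoints will be followed daily during treatment". That sentence concerns when clinicians may extend treatment. It does not name CPIS or say that scoring ends. Section IX schedules CPIS throughout enrolment. Section X adds "Please see the attached data collection tool for detailed information", and that form is not in the text available here, so its absence is no evidence of a gap.
- *A repeated-measures mixed model is required.* The calculations compare an unadjusted with a baseline-adjusted summary. They do not show that a model with arm-by-day terms beats ANCOVA on one named summary.
- *The planned tests inflate type I error through correlated daily scores.* That would need patient-days pooled as independent or each day tested separately, and the plan proposes neither.

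**Conclusion.** The point holds as a matter of efficiency and prespecification. Section XII names no CPIS summary and does not assure adjustment for CPIS at randomization. Unconditional adjustment lowered variance under every correlation structure tried. For the day 5-10 mean the illustrative gain is 0.17 to 0.18 in power (0.76 to 0.94, or 0.69 to 0.87). For the day 5-18 mean under AR(1) 0.8 it is 0.08. These sizes rest on assumed correlations, an assumed 0.2 SD effect and complete scores. Neither co-primary outcome is affected. The change is worth making because it costs little, not because the present analysis would mislead.

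**What to change.** Add one paragraph to Section XII:
- Name one post-randomization CPIS summary over one window, counted from the start of appropriate therapy and identical in both arms. The mean of days 5-10 is an example: it begins after the latest permitted randomization. The investigators should choose the length knowing that a short window misses later differences and a long one meets more death and discharge.
- Compare arms by ANCOVA on the last CPIS before randomization, with center in the model, whether or not imbalance is seen. A repeated-measures mixed model with the same baseline covariate is an acceptable alternative.
- Use a rank-based ANCOVA if the bounded score is clearly non-normal.
- State how scores missing after death, discharge or extubation are handled, with one sensitivity analysis. Extubation needs naming because every patient is still intubated at randomization (Section V, exclusion m).

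The cost is the paragraph and slightly more analysis work. No new data are needed if CPIS is scored throughout enrolment, as Section IX says, and the case report form captures a score before randomization; the second condition should be confirmed.
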